16.2. Clinical Function

16.2.1. Methods of Analysis

As this is an open-label, long-term extension study, analyses will be exploratory and descriptive in nature.

Data will be summarized using descriptive statistics for continuous variables and using frequency and percentage for discrete variables. For participants who have completed Parts A or B of Study 233AS101, the time trajectory of each clinical function may be summarized at selected timepoints and presented in plots. For participants who have completed Part C of Study 233AS101, the time trajectory will be summarized by the prespecified subgroup (enriched population versus other eligible participants) and the prior treatment received during Study

CONFIDENTIAL

The information contained herein may not be used, disclosed, or published without the written consent of Biogen MA Inc.

233AS101 from the baseline of Study 233AS101 (including data from Studies 233AS101 and 233AS102), from the baseline of Study 233AS102 (including data from Study 233AS102 only), and from the start of BIIB067 100 mg dosing.

Efficacy will be measured based on changes in ALSFRS-R, percent predicted SVC, HHD Megascore and individual muscle strength, [REDACTED]. Changes from baseline (using definitions outlined above) will be summarized over time for each of these endpoints.

Analysis of covariance using multiple imputation will be performed at selected timepoints, based on level of data available at interim and final analysis.

Time to death or permanent ventilation (i.e., ≥ 22 hours of mechanical ventilation [invasive or noninvasive] per day for ≥ 21 consecutive days) and time to death will be summarized using Kaplan-Meier curves based on the starting time using the following:

1. Entry into Study 233AS101
2. Entry into Study 233AS102
3. The start of BIIB067 100 mg dosing
4. Time of symptom onset

The relationship between PK or PD endpoints and the clinical function endpoints will also be explored.

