4.12. Immunogenicity Data

The immunogenicity population will be used for all analyses of immunogenicity data.

- For immunogenicity, the baseline value is defined as the latest immunogenicity data collected at any time prior to the first dose in 233AS102. If no immunogenicity data are collected immediately prior to the first dose in 233AS102, the baseline value is missing and will be imputed as anti-drug antibody negative for immunogenicity analyses.
- Subjects with at least one confirmed post-treatment positive result will be considered treatment-emergent positive for anti-drug antibodies if their baseline result is negative.
- Subjects where none of the post-treatment samples were positive for anti-drug antibodies will be considered negative regardless of their baseline result.
- For subjects who are confirmed positive at baseline and have at least one post-treatment sample with a ≥ 2 -fold increase in titer will be considered positive for anti-drug antibodies. Subjects that are positive at baseline, with subsequent post-treatment samples titers that are within 2-fold will be considered negative for anti-drug antibodies. If there

are any samples which the lab was able to confirm the screen was ADA positive but could not determine the magnitude of the positive response in time for interim datacut off date these will be considered as being ≥ 2 -fold for the purpose of this analysis.

Number and percentage of subjects who has positive result and negative result at baseline, subjects with any post-baseline positive result and negative result, subjects with any positive ADA will be summarized by prior treatment groups.

In addition, for subjects that are considered anti-drug antibody positive with immunogenicity data, the following may be evaluated:

- o Persistent anti-drug antibody response:
 - More than one positive time point that are ≥ 112 days apart
 - or
 - One or more positive time point, but < 112 days of evaluable data post first positive time point.
- o Transient anti-drug antibody response:
 - A single positive time point, followed by ≥ 112 days results which are all negative.

Or

- Two or more positive data points with < 112 days apart, with later negative samples that are ≥ 112 days apart from the first positive result.

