- o Caveat: Since the data are only being considered from baseline of 233AS102, a subject who became persistent in 101 will not be accounted for as persistent based on their prior data in 233AS101. Therefore, the subject could be summarized as being transient if there is no change in their titer in 233AS102.
- o If a subject has just one positive postbaseline ADA in 233AS102 at last available assessment at the time of Interim cutoff date and is still ongoing, then this subject will be summarized as transient.

Number and percentage of subjects who have persistent ADA result and transient ADA result will also be summarized by prior treatment groups.

The incidence of AEs selected by anaphylactic reaction SMQ, angioedema SMQ, and hypersensitivity SMQ will also be presented for subjects with at least 1 positive ADA result at post-baseline by prior treatment groups. Percentages will be calculated out of the immunogenicity population.

The incidence of AEs selected by anaphylactic reaction SMQ, angioedema SMQ, and hypersensitivity SMQ will also be presented for subjects with negative ADA result at post-

baseline by prior treatment groups. Percentages will be calculated out of the immunogenicity population.

5. Changes to Planned Analyses

- Analysis of efficacy, [REDACTED] and biomarker endpoints are specified in the Protocol; however, they will not be included in 233AS102 final CSR but will be included under the integrated analyses of 233AS101 and 233AS102. Analyses of efficacy and biomarker endpoints conducted for interim data (July 2021 and January 2022) highlighted the limitations of conducting standalone 233AS102 analyses in these endpoints as outlined in section 1. Based on these learnings, it only makes sense to analyze the longitudinal data from 233AS102 for efficacy and biomarker endpoints as part of an integrated analysis of 233AS101 and 233AS102. The analyses from 233AS102 baseline specified in the protocol will therefore not be appropriate and will not be conducted; analyses from other baseline definitions will be discussed in the ISE SAP.

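### A subject who is antibody positive at 233AS102 baseline and stays positive at a stable titre is classed as negative by one rule in SAP 4.12 and possibly transient by a caveat, and fits neither transient definition

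*SAP*

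**What the plan says.** All the rules are in SAP 4.12.

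- **Overall status.** A baseline-negative subject with a confirmed later positive is treatment-emergent positive. A baseline-positive subject counts as positive only if at least one later sample shows a rise in titre of 2-fold or more. Otherwise: "Subjects that are positive at baseline, with subsequent post-treatment samples titers that are within 2-fold will be considered negative for anti-drug antibodies".
- **Who enters the split.** The persistent/transient classification applies "for subjects that are considered anti-drug antibody positive with immunogenicity data, the following may be evaluated".
- **Persistent.** There are two definitions. The first is "More than one positive time point that are ≥ 112 days apart". The second covers a subject with at least one positive whose usable follow-up after the first positive is shorter than 112 days.
- **Transient.** There are again two. The first is one positive with nothing but negatives over at least the next 112 days. The second reads "Two or more positive data points with < 112 days apart, with later negative samples", where the negatives must lie at least 112 days after the first positive.
- **Caveat.** Persistence established in 233AS101 is not carried forward. The SAP concludes: "Therefore, the subject could be summarized as being transient if there is no change in their titer in 233AS102".
- **Interim bullet.** A subject still ongoing at the interim cutoff, whose only post-baseline positive is the last available sample, is summarised as transient.

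The persistent and transient counts are reported by prior treatment group.

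**The concern.** The caveat describes a subject who is already positive on entering 233AS102 and whose titre then does not move. The overall-status rule has already made that subject negative, so no persistent/transient label should follow. If a label is given anyway, transient is the one the subject cannot satisfy. Two programmers working from this section could produce different tables, and both would describe a continuously positive subject as something else.

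The effect is unlikely to be even across columns. SAP section 1 notes that some Part C subjects enter tofersen-naive and others after about 6 months of tofersen. Drug-induced ADA present at 233AS102 baseline can therefore arise in the prior-tofersen group but hardly in the prior-placebo group. A prior-placebo subject who seroconverts in 233AS102 and stays positive is counted as persistent. A prior-tofersen subject with the same run of positives, who seroconverted in 233AS101, is counted as negative or perhaps transient. A reader comparing the two columns could see less persistent ADA in the prior-tofersen group because of the rule alone.

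**Working it through.** There is no sample size, power or event figure to reproduce here. The check is to pass one subject through the rules.

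**Inputs.** ADA samples are taken on Days 1, 15 and 29, at Week 12, and every 8 weeks thereafter to Week 356 (Schedule of Activities, footnote 18). Target day = 7 × week + 1, which gives Week 12 = Day 85, Week 20 = Day 141 and Week 28 = Day 197, in agreement with SAP Tables 3 and 5. The test subject is positive on Day 1 and positive at the same titre at every later sample.

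| Rule in SAP 4.12 | Result for this subject |
|---|---|
| Overall status (titre within 2-fold) | Negative |
| Entry to persistent/transient split | Not entered, because not ADA positive |
| Transient, first definition (one positive, then negatives) | Not met: more than one positive and no negatives |
| Transient, second definition (positives under 112 days apart, then negatives) | Not met: no negatives |
| Caveat | Could be transient |
| 112-day wording read on raw results, ignoring the entry condition | Persistent |

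**Last row.** The spacing from Day 15 to Day 141 is 141 − 15 = 126 days, and from Day 29 to Day 141 it is 141 − 29 = 112 days. From the Week 20 sample onward the first persistent definition is met. If the last sample is earlier (Day 85 at the latest), there are at most 85 − 15 = 70 days of data after the first post-baseline positive, so the second persistent definition applies. Transient is not reached at any length of follow-up.

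**A reading that might rescue the caveat.** Suppose a time point counts as positive only if its titre is at least 2-fold above baseline. A subject with no change in titre then has no positive time point, and both transient definitions require at least one. The caveat still does not fit.

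**Dependence on the baseline sample.** A missing baseline is imputed as negative. The same later results then make the subject treatment-emergent positive and persistent, so one missing sample moves the label from negative to persistent.

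**Interim bullet.** A single positive at the last sample has no later data, that is, under 112 days. The second persistent definition calls it persistent; the bullet calls it transient.

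**Possible size (assumed, since no ADA rates are given).** Let s be the share of prior-tofersen subjects with a persistent response on raw results who were already positive at baseline with a stable titre, and m the share of those with a missing baseline sample. Following the entry condition strictly, reported persistent ÷ raw persistent = 1 − s(1 − m).

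| s | m = 0 | m = 20% |
|---|---|---|
| 25% | 75% | 80% |
| 50% | 50% | 60% |
| 75% | 25% | 40% |

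For prior-placebo subjects, s should be close to zero.

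**The case against.** Several points on the other side stand.

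- **The rules in order give one label.** A reader might infer that the SAP gives this subject three labels: negative, transient and persistent. It does not. The entry condition removes the subject before the 112-day definitions are applied, so persistent is only what the wording describes on raw results. The conflict is between the caveat on one side and the entry condition and transient definitions on the other.
- **Negative has a defensible meaning.** An unchanged titre marks no new or boosted response in 233AS102. That is worth reporting, but under a name that does not suggest absence of antibody.
- **The subjects are not hidden.** SAP 4.12 also counts subjects positive at baseline and subjects with any post-baseline positive. The hypersensitivity, angioedema and anaphylaxis tables are worded on post-baseline positive results, which these subjects have.
- **Other rules push counts up.** Missing baselines are imputed negative, titres not determined in time are taken as at least 2-fold, and a single rise of 2-fold or more makes the subject positive.
- **Scope is disclosed.** The SAP says that 233AS101 persistence is not counted, and Protocol 16.1 foresees pooled immunogenicity plans. That limits the reach of the problem to the standalone report; it does not reconcile the caveat with the definitions.
- **The stakes are moderate.** The protocol describes its clinical function work by saying that "analyses will be exploratory and descriptive in nature" (16.2.1), SAP 4.1 provides descriptive summaries, and immunogenicity is not among the primary or secondary endpoints listed in SAP 2.1.
- **The interim bullet should have little effect at closeout.** SAP Version 4.0 is for the final report, when the interim cutoff no longer governs.

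**Conclusion.** The section is wrong as written for baseline-positive, stable-titre subjects: the caveat suggests a label whose definition they cannot meet, and the overall rule reports continuously positive subjects as negative. Ongoing or persistent ADA may be undercounted in the standalone table, mainly in the prior-tofersen Part C column. This rests on some prior-tofersen subjects being positive at entry with a titre that stays within 2-fold at every sample. The documents give no count, so the direction is likely but the amount is unknown; the fractions above are illustrations.

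A reader might go further and say that persistence is shown to be under-reported in the group with the longest exposure, in subjects positive for years. The documents do not support this. Prior-tofersen subjects have about 6 months more exposure than prior-placebo subjects within Part C, but Parts A and B subjects were in 233AS102 before Part C enrolment began (SAP 2.3). Neither exposure by group nor duration of positivity is given.

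**What to change.** In SAP 4.12:

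1. Delete the caveat sentence that allows a stable-titre subject to be summarised as transient.
2. Delete the interim-cutoff bullet, which conflicts with the second persistent definition and has no role at closeout.
3. Keep new ADA, or ADA boosted 2-fold or more, as the line for treatment-emergent response in 233AS102.
4. Move subjects who are positive at baseline with titre within 2-fold out of the negative count to their own row, by prior treatment group, and apply the 112-day definitions to their confirmed positives.
5. For Part C subjects only, who had no washout, allow 233AS101 Part C samples taken after the first tofersen dose to be used when judging persistence. Do not link positives across the Parts A/B washout: SAP section 1 puts it at 16 weeks to over 2 years, so positives far apart could be called persistent without samples between them.

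Items 1 to 4 cost wording and one extra table row. Item 5 also needs the Part C antibody results brought into the analysis dataset. The reported ADA-positive and persistent percentages would rise slightly.

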7.2. Overall Study Duration and Follow-Up

The overall duration of study participation for a single participant will be up to 368 weeks, which includes an approximately 4-week screening period, up to a 360-week treatment period, and a 4-week follow-up period.

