7.2.2.2. Maintenance Dose Period

During the maintenance portion of the study, participants will receive up to 90 doses of BIIB067, approximately every 4 weeks, during visits at Weeks 8, 12, and 16 and every 4 weeks thereafter until the last participant enrolled has had the opportunity to have their Week 152 Maintenance Dose Visit.

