3.5. Analysis Sets

ITT Population

The ITT population is defined as all subjects who enrolled and received at least one dose of study treatment in 233AS102.

Safety Population

The safety population is defined as all subjects who enrolled and received at least one dose of study treatment in 233AS102 (i.e. the overall ITT population of subjects).

Pharmacokinetic (PK) Population

The PK population is defined as all subjects who received at least one dose of study treatment and have at least one post-dosing PK concentration measurement in 233AS102.

Immunogenicity Population

The analysis population for immunogenicity is defined as all subjects who received at least one dose of study treatment and have at least 1 post-dosing sample evaluated for immunogenicity in 233AS102.

Populations used for analysis

Efficacy endpoints and PD/biomarker endpoints will not be summarized in 233AS102 standalone analysis and final CSR, but these data will be combined with data from 233AS101 and analyzed based on the ISE SAP.

The analysis of plasma and CSF PK concentration of tofersen will be analyzed using the PK population. All safety evaluations will be summarized using the safety population.

4. Statistical Methods for Planned Analyses

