4.9.1. Adverse Events

All AEs will be classified using MedDRA version 27.0 or later. All AEs will be listed but only treatment emergent AEs will be summarized, where treatment emergence will be relative to the first dose of study drug. A treatment emergent AE/SAE is defined as any AE/SAE with an onset date and time that is on or after the first dose of study drug or any pre-existing condition that has worsened in severity after the first dose of study drug. In case of missing dates,

- Any AE/SAE with both a missing onset date and resolution date, or any AE/SAE with a missing onset date and a resolution date which is after the first dose of study drug, will be considered treatment emergent.
- If the onset date is available but onset time is missing and the AE onset date is the same as the first dose date the AE will be considered treatment emergent.
- For AEs with a partial start date, the year/month of the event date will be compared to that of the first dose date to determine whether the event is treatment emergent.

The incidence of treatment emergent AEs will be summarized by study group as follows:

- by primary system organ class (SOC) and MedDRA preferred term sorted by decreasing frequency
- by SOC and MedDRA preferred term sorted by alphabetical order
- by MedDRA preferred term
- by SOC

- The most common treatment emergent AEs i.e. occurring in $\geq 5\%$ subjects in any study group will be presented by MedDRA preferred term.
- For Part C subjects only, the most common treatment emergent AEs i.e. occurring in 2 or more subjects in subjects previously on tofersen in 233AS101 compared to subjects who were on placebo will be presented by MedDRA preferred term.
- By maximum CTCAE grade, primary SOC and MedDRA preferred term
- By maximum CTCAE grade and MedDRA preferred term
- AEs with a CTCAE grade ≥ 3 by primary SOC and MedDRA preferred term
- Related AEs by primary SOC and MedDRA preferred term
- SAEs by primary SOC and MedDRA preferred term
- SAEs by MedDRA preferred term
- Related SAEs by primary SOC and MedDRA preferred term
- AEs related to lumbar puncture (as assessed by the investigator) by primary SOC and MedDRA preferred term
- AEs that occurred within 24 hours of dosing by primary SOC and MedDRA preferred term (in case of partial AE start date, if the month and year are available and day is missing, the AE will be included for any dose that occurs in the same month and year as the AE)

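### The adverse event tables by anti-drug antibody (ADA) status ignore event timing and unequal follow-up, and their shared denominator means the percentages are not risks by ADA status

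*SAP*

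**What the plan says.** SAP 4.12 plans a table of events from three standardised MedDRA queries (anaphylactic reaction, angioedema, hypersensitivity) that "will also be presented for subjects with at least 1 positive ADA result at post-baseline by prior treatment groups". A companion table of the same events "will also be presented for subjects with negative ADA result at" post-baseline. For each table, "Percentages will be calculated out of the immunogenicity population".

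That population (SAP 3.5) needs one dose and must "have at least 1 post-dosing sample evaluated for immunogenicity in 233AS102"; there is no minimum follow-up. Under SAP 4.9.1, "only treatment emergent AEs will be summarized, where treatment emergence will be relative to the first dose of study drug", so event counting starts before any post-baseline antibody result exists.

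Follow-up varies by design. Protocol 7.2 allows "up to a 360-week treatment period, and a 4-week follow-up period", while Protocol 7.2.2.2 continues dosing "until the last participant enrolled has had the opportunity to have their Week 152 Maintenance Dose Visit". SAP Section 1 also reports many discontinuations among subjects from Parts A and B. SAP 4.9.1 plans follow-up-adjusted and exposure-adjusted incidence rates, but by study group and not by ADA status.

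Earlier in SAP 4.12 there is a separate ADA status rule. A subject who is positive at baseline and whose later titres stay within 2-fold is classed as negative. A subject with no positive post-treatment sample is also classed as negative.

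**The concern.** These are the only tables in this SAP that set antibody status beside the events antibodies might cause, so readers will use them to judge whether there is a link. Three features get in the way.

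- **Denominator.** Neither percentage is a risk among ADA-positive or ADA-negative subjects.
- **Follow-up.** A subject followed longer has more samples that can turn positive and more time to have an event. The schedule gives 20 post-baseline samples by Week 152 (Days 15 and 29, then 18 from Week 12 to Week 148) and 46 by Week 360, plus the final visit.
- **Timing.** An event before the first positive sample is counted under ADA-positive.

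The two groups are also not clearly separate. Read literally, a subject with one positive and one negative post-baseline sample fits both tables. A baseline-positive subject with a stable titre is negative under the status rule, yet can have a positive post-baseline result.

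**Working it through.** The documents give no ADA incidence, no incidence of these events and no follow-up distribution, so there is no figure of the plan's own to reproduce. All rates below are assumptions.

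**Inputs.** From the documents: the ADA sampling schedule, a shortest completed follow-up of 152 + 4 = 156 weeks and a longest of 360 + 4 = 364 weeks. Assumed: 10, 30 or 60% of subjects ADA-positive and 5, 10 or 20% with an event by 156 weeks, with constant hazards. ADA onset and event onset are independent, so the true ratio is 1.

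**Step 1: what the planned display shows under equal follow-up.** With ADA probability p and event probability q, the two printed percentages are p × q and (1 − p) × q. For q = 10%:
- p = 10%: 1.0% and 9.0%
- p = 30%: 3.0% and 7.0%
- p = 60%: 6.0% and 4.0%

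The contrast reflects p only.

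**Step 2: re-basing with two follow-up lengths, by hand.** Suppose half the subjects are followed for 156 weeks and half for 364, with p = 30% and q = 10% at 156 weeks.
- At 364 weeks, ADA: 1 − 0.7^(364/156) = 0.565. Event: 1 − 0.9^(364/156) = 0.218.
- Event risk, ever positive: (0.3 × 0.1 + 0.565 × 0.218) / (0.3 + 0.565) = 0.153 / 0.865 = 0.177.
- Event risk, never positive: (0.7 × 0.1 + 0.435 × 0.218) / (0.7 + 0.435) = 0.165 / 1.135 = 0.145.
- Ratio: 0.177 / 0.145 = 1.22, with no true effect and no early dropout.

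**Step 3: simulation on the planned sampling grid** (2,000,000 subjects per scenario). Mixed follow-up means that 40% leave at 4–156 weeks and 60% are followed for 156–364 weeks. For q = 10%:

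| ADA by 156 weeks | Printed, mixed follow-up (positive / negative) | Re-based ratio, mixed | Re-based ratio, equal |
|---|---|---|---|
| 10% | 1.8% / 9.9% | 1.33 | 1.00 |
| 30% | 4.8% / 6.8% | 1.43 | 1.01 |
| 60% | 8.5% / 3.2% | 1.73 | 1.00 |

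Over all the assumed rates, the re-based ratio was 1.30–1.46 with follow-up uniform over 4–156 weeks, 1.32–1.76 with mixed follow-up and 1.31–1.78 with follow-up uniform over 4–364 weeks. It was 0.98–1.01 when everyone was followed for 156 weeks. Other assumed hazards and follow-up patterns widen the range under unequal follow-up to roughly 1.2–1.9.

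**Step 4: the separate effect of timing.** With equal follow-up, 45–53% of the events counted under ADA-positive began before the first positive sample, yet the null ratio stayed at about 1. The damage appears when the effect is real: a true hazard ratio of 3 gave 1.93 (ADA 30%) and 2.01 (ADA 60%). With mixed follow-up the two biases pull in opposite directions, and the same true ratio gave 2.7 and 3.47.

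**Step 5: the remedy.** Assigning both events and person-time to ADA status at that moment gave null rate ratios of 0.98–1.02 in every scenario.

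**Step 6: a tempting shortcut.** Suppose the positive row keeps only events from the first positive sample onward, while never-positive subjects keep all of theirs. With subgroup denominators the null ratio was then 0.47–0.57 under equal 3-year follow-up and 0.63–1.20 under unequal follow-up. This is immortal-time bias, and in many settings it would hide a real risk.

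**The case against.** The best defence is that the SAP only tabulates. Its summaries are descriptive (SAP 4.1), and no test, estimate or causal statement about antibodies and events is planned. That is right. A reader might infer that the plan attributes events before seroconversion to antibodies, but nothing in SAP 4.12 does so.

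A second defence is that the false ratio does not belong to the printed table. It needs subgroup denominators, and the SAP sets a common one. This also stands. A reader might conclude that the planned output is biased toward a positive association, but the printed percentages can point either way. That does not rescue the display: the printed figures do not answer the question, and the natural way to make them do so brings in the bias.

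Third, the share of events before positivity might be taken as proof of a false association. It is not. With equal follow-up that share is about half and the null ratio is about 1. Unequal follow-up creates the false association; ignoring timing dilutes a real one.

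Fourth, the status rule in SAP 4.12 already defines negative subjects, which narrows the overlap. The event tables do not refer to that rule, and their wording for the positive group departs from it.

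Finally, subjects already positive on entry have no pre-conversion time in this study. Some may have come from the prior tofersen group. The simulations start everyone negative, so they do not describe these subjects.

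**Conclusion.** The concern holds in a limited form. The two tables do not give event risks by ADA status, and no adjustment for timing or follow-up by ADA status is planned. As printed, the percentages mostly track ADA prevalence. Re-based, they show a ratio of roughly 1.2 to 1.9 under no effect when follow-up is unequal. With equal follow-up, a true hazard ratio of 3 shrinks to about 2.

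The sizes rest on assumed ADA rates, event rates and follow-up patterns, with constant hazards. The direction under unequal follow-up did not change across them.

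A reader might also infer that this is the sponsor's only look at antibodies and these events. The documents do not support that: Protocol 16.1 and SAP Section 1 refer to integrated plans, which are not available here. The statement holds for this SAP only.

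**What to change.** - State one ADA status definition for all of SAP 4.12, consistent with its existing rule. Say explicitly where stable-titre baseline positives belong, and make the groups mutually exclusive.
- Replace the two percentage tables with events per person-year by time-dependent ADA status. Events and time before the first positive sample, and all time in never-positive subjects, count as ADA-negative. Events and time from the first positive sample onward count as ADA-positive. A subject who converts contributes to both.
- Add a listing of event day against first-positive day for every subject with one of these events.
- Do not simply remove earlier events from the positive row, for the reason in step 6 of the working.

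The cost is a wording change, one reprogrammed table and one listing. Sample and event dates are already collected, and SAP 4.9.1 already defines person-time rates. The drawback is small counts: at most 183 subjects were to be dosed in the parent study, and the table is split by prior treatment group. The listing may therefore be the more informative output.
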